6.1 Study treatment

The investigational treatment for this study is asciminib (40 mg b.i.d. or 80 mg q.d. as assigned by IRT). Novartis will supply asciminib to the investigational site as 20 mg and 40 mg tablets.

In patients not achieving MMR at 48 weeks or losing the response (confirmed loss of MMR in two consecutive tests) after the week 48 assessment up to week 108, asciminib dose may be escalated to 200 mg q.d. if in the investigator's opinion the patient may benefit from the escalation. In addition, to participate in the dose escalation, there must not be any grade 3 or 4 toxicity while on therapy, or persistent grade 2 toxicity, possibly related to asciminib and unresponsive to optimal management.

Dose escalation may happen at next schedule visit upon receipt of BCR-ABL1 and **CCI** [REDACTED].

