Study visits from Week 1 Day 1 to Week 2 Day 1 should be completed on the designated date [with an allowed "visit window" of +/- 1 day for Week 1 Day 1 and Week 2 Day 1]

Study visits from Week 4 to Week 12 should be completed every 4 weeks on the designated date [with an allowed "visit window" of +/- 2 day]

Study visits after Week 12 (from Week 24) to EOT should be completed every 12 weeks on the designated date [with an allowed "visit window" of +/- 7 days].

Safety follow-up should be completed 30 days from the last dose of study treatment [with an allowed "visit window" of +/- 7 days].

Visit at weeks 62, 74, 86, 98, 110 or 122 that is two weeks post dose escalation should be completed once after dose escalation on the designated date [with an allowed "visit window" of +/- 1 day].

A delayed visit will have no impact on the next planned visit. The next visit should be completed as scheduled in order to avoid accumulation of additional weeks.

Visit name	Category	Protocol Section	Screening Phase	Treatment Phase										EOT (week 144) /Early Discontinuation	Safety follow-up ¹³		
				Screening/ Baseline	Week 1 Day 1	Week 2 Day 1	Week 4	Week 8	Week 12	Week 24	Week 36	Week 48	Every 12 weeks up to week 132 (w60, w72, w84, w96, w108, w120, w132)			Week 62/74/86/98/ 110/122 for patient dose escalating	
Days (+/- X days)			Day -28 to -1	1 (+/- 1 day)	8 (+/- 1 day)	29 (+/- 2 days)	57 (+/- 2 days)	85 (+/- 2 days)	169 (+/- 7 days)	253 (+/- 7 days)	337 (+/- 7 days)	(+/- 7 days)	(+/- 1 day)	(+/- 7 days)	(+/- 7 days)		
Prior/concomitant medications	D	8.2	X	Continuous													
Physical Examinations	S	8.4	X	X		X	X	X	X	X	X	X		X			
Extra medullary Involvement	D		X														
ECOG Performance status	D	8.4.1	X	X		X	X	X	X	X	X	X		X			
Height	D	8.4	X														
Weight	D	8.4	X	X				X	X	X	X	X		X			
Vital signs ¹	D	8.4	X	X	X	X	X	X	X	X	X	X		X			
Laboratory assessments		8.4.2															
Hematology	D	8.4.2	X	X	X	X	X	X	X	X	X	X	X	X			
Chemistry ²	D	8.4.2	X	X	X	X	X	X	X	X	X	X	X	X			
Coagulation	D	8.4.2	X	As clinically indicated													

1. Blood Pressure reading to be taken in the supine position for all visits.
2. Hemoglobin A1c to be collected at screening only.

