8.3.1.1 Molecular response

Molecular response (MR) will be assessed in all patients.

Levels of BCR-ABL1 transcripts will be determined by real-time quantitative PCR (RQ-PCR) testing of peripheral blood and analyzed centrally. Log reduction in BCR- ABL1 transcripts levels from the standardized baseline value, or the percent ratio of BCR-ABL1 transcripts versus control gene (ABL1) transcripts converted to a reference standard, international scale (IS) ([Hughes and Branford 2006](#)), will be calculated for each sample.

Major molecular response and related variables are defined as the following:

- Rate of MMR where MMR is defined as a ≥ 3.0 log reduction in BCR-ABL1 transcripts compared to the standardized baseline equivalent to ≤ 0.1 % BCR-ABL1/ABL1 % by IS as measured by RQ-PCR, confirmed by duplicate analysis of the same sample,
- Time to MMR defined as the time from the date of enrollment to the date of the first documented MMR,
- Duration of MMR defined as the time from the date of first documented MMR to the earliest date of loss of MMR, progression to AP or BC, or CML-related death.
- Rate of Deep Molecular Responses MR4 and MR4.5 are defined as a ≥ 4 log or ≥ 4.5 log reduction in BCR-ABL1 transcripts compared to the standard baseline equivalent to 0.01 % or 0.0032% BCR-ABL1/ABL by IS as measured by RQ-PCR, confirmed by duplicate analysis of the same sample with at least 10,000 or 32,000 ABL1 transcripts, respectively.

Loss of MMR is defined as increase of BCR-ABL1/ABL to $> 0.1\%$ by international scale (IS) in association with a ≥ 5 -fold rise in BCR-ABL1 from the lowest value achieved on study

treatment and replicated by a second analysis of the same sample. Loss of MMR confirmed by subsequent sample analysis within 4 to 6 weeks showing loss of MMR associated with a ≥ 5 -fold rise in BCR-ABL1 from the lowest value achieved on study treatment, unless it is associated with confirmed loss of CHR or loss of CCyR or progression to AP/BC or CML-related death. The blood samples will be taken as described in [Table 8-1](#) and [Table 8-2](#).

If at one visit the sample is missing during transit to the central PCR laboratory, or the PCR result is difficult to interpret or sample not analyzable, or if the PCR sample was not collected, a subsequent unscheduled visit sample must be collected within 4 weeks either at the next scheduled visit (week 4 or week 8) or as an unscheduled visit.

Table 8-2 Blood samples (efficacy primary endpoint)

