Sample Type	Volume	Visit
Blood for BCR-ABL1 quantification by RQ-PCR	20 mL	Screening/Baseline
	20 mL	Week 12
	20 mL	Week 24
	20 mL	Week 36
	20 mL	Week 48
	20 mL	Every 12 weeks thereafter up to week 132 (w60, w72, w84, w96, w108, w120, w132)
	20 mL	End of Treatment

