8.4.2 Laboratory evaluations

Central laboratory will be used for analysis of hematology, biochemistry, coagulation, serum pregnancy and hepatitis marker specimens collected (safety monitoring) as specified in [Table 8-1](#). The time windows granted for laboratory evaluations are identical with the corresponding visit time windows for each visit (see [Section 8](#)).

Additional unscheduled blood draws may be performed at the discretion of the investigator at any time during the study. For example, if the PCR sample was lost during transit or result is difficult to analyze, to confirm a loss of response to study treatment or as clinically indicated.

If the COVID-19 pandemic limits or prevents on-site study visits, if pre-agreed with Novartis and considered by the Investigator it is in the interest of the participant's health to perform study procedures remotely, safety samples that can be collected remotely will be collected and analyzed in line with the study laboratory manual. If participants cannot visit the site for protocol specified safety lab assessments or in case of central lab logistical challenges an alternative laboratory (local) collection site may be used. Please note that BCR-ABL1 quantification must be performed centrally. Where samples are collected and analyzed at a local laboratory instead of the central laboratory, Novartis will ensure the results reported for

hematology and chemistry described below are equivalent to central laboratory collection and analysis by collecting the local normal ranges.

Table 8-5 Central clinical laboratory parameters collection plan

Test category	Test Name
Hematology	Hemoglobin, platelets, red blood cells, white blood cells, WBC morphology with differential (basophils, eosinophils, lymphocytes, monocytes, neutrophils, promyelocytes, myelocytes, metamyelocytes, blast and other)
Chemistry	Albumin, alkaline phosphatase, ALT (SGPT), AST (SGOT), total calcium, total calcium (corrected for albumin), creatinine, creatine kinase, potassium, magnesium, sodium, phosphate (inorganic phosphorus), direct bilirubin, indirect bilirubin, total bilirubin, total cholesterol, LDL cholesterol, HDL cholesterol, total protein, triglycerides, blood urea or Blood Urea Nitrogen (BUN), uric acid, amylase, lipase, serum glucose (fasting), Hemoglobin A1c (at screening only), Creatinine clearance (Cockcroft-Gault formula)
Coagulation	International Normalized Ratio (INR), Activated Partial Thromboplastin Time (aPTT)

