2.6.1.1 Molecular response

MMR rates at all scheduled data collection time points, i.e., the protocol-planned visits except for 48 weeks which is already covered by primary endpoint. Such rates are defined as the proportion of subjects with MMR at the respective time points.

MMR rates by all scheduled data collection time points, i.e., the protocol-planned visits. These are cumulative MMR rates by time points and are defined as the proportion of subjects who achieve MMR at or before specified visits, i.e. if a subject achieves an MMR but then loses it before or at a specific visit, he/she will still be classed as achieving MMR by that specific time point. Subjects without any documented response for which an evaluable response assessment was never provided will be considered as non-responders for the period of time up to that time point.

Molecular response category at specific time points, i.e., the protocol-planned visits. Categories of molecular response are defined in Appendix.

Molecular response category by specific time points, i.e., the protocol-planned visits. This is defined as the molecular response category up to the specific time points.

Time to MMR (in weeks) is defined as: $(\text{date of first documented MMR} - \text{date of randomization} + 1)/7$.

Duration of MMR is defined in protocol section 8.3.1.1 as the time from the date of first documented MMR to the earliest date of confirmed loss of MMR, progression to accelerated phase (AP) or blast crisis (BC), or CML-related death. Loss of MMR and progression to accelerated phase (AP)/blast crisis (BC) are defined in Appendix.

The duration of MMR (in weeks) is calculated as: $(\text{end date or censoring date of MMR} - \text{date of first MMR} + 1)/7$.

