- Duration of MMR defined as the time from the date of first documented MMR to the earliest date of loss of MMR, progression to AP or BC, or CML-related death.
- Rate of Deep Molecular Responses MR4 and MR4.5 are defined as a ≥ 4 log or ≥ 4.5 log reduction in BCR::ABL1 transcripts compared to the standard baseline equivalent to 0.01 % or 0.0032% BCR::ABL1/ABL by IS as measured by RQ-PCR, confirmed by duplicate analysis of the same sample with at least 10,000 or 32,000 ABL1 transcripts, respectively.

Loss of MMR is defined as increase of BCR::ABL1/ABL to $> 0.1\%$ by international scale (IS) in association with a ≥ 5 -fold rise in BCR::ABL1 from the lowest value achieved on study treatment and replicated by a second analysis of the same sample. Confirmed loss of MMR by subsequent sample analysis within 4 to 6 weeks showing loss of MMR associated with a ≥ 5 -fold rise in BCR::ABL1 from the lowest value achieved on study treatment, unless it is associated with confirmed loss of CHR or loss of CCyR or progression to AP/BC or CML-related death.

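### Loss of MMR must be confirmed within 4 to 6 weeks, but scheduled PCRs are 12 weeks apart, so duration of MMR and related endpoints may be overstated where no unscheduled draw is taken

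*SAP*

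**What the plan says.** **Confirmation rule.** SAP 5.4.1 requires "Confirmed loss of MMR by subsequent sample analysis within 4 to 6 weeks showing loss of MMR". Protocol 8.3.1.1 matches it: "Loss of MMR confirmed by subsequent sample analysis within 4 to 6 weeks showing loss of MMR". Both waive the second sample in some cases. In the SAP's words: "unless it is associated with confirmed loss of CHR or loss of CCyR or progression to AP/BC or CML-related death".

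**PCR schedule.** Table 8-2 in protocol 8.3.1.1 lists PCRs at screening and Weeks 12, 24, 36 and 48, then "Every 12 weeks thereafter up to week 132 (w60, w72, w84, w96, w108, w120, w132", and at end of treatment. Protocol Section 8 says: "Study visits after Week 12 (from Week 24) to EOT should be completed every 12 weeks on the designated date", with a window of 7 days either side. The Week 12 window is 2 days either side. The sampling table contains no confirmatory visit.

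**Unscheduled samples.** Protocol 8.4.2: "Additional unscheduled blood draws may be performed at the discretion of the investigator at any time during the study". Confirming a loss of response is one of the examples it gives. SAP 2.1.1 uses unscheduled results, but excludes efficacy assessments after the EoT visit (except for OS and PFS).

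**Event definitions.** SAP 2.6.1.1 and 2.6.2 end duration of MMR at the "earliest date of confirmed loss of MMR" (or AP/BC or CML-related death) and attribute this to protocol 8.3.1.1. The duration definition there, and those in protocol 12.5.1, SAP Table 1-1 and SAP 5.4.1, refer to loss of MMR without *confirmed*. SAP 2.6.1.3 and 5.4.4 list confirmed loss among the treatment-failure events. Patients without an event are censored at their last on-treatment PCR.

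**Dose escalation.** Protocol 6.1 describes patients "losing the response (confirmed loss of MMR in two consecutive tests" with no time limit between tests. Protocol 6.6.2 and 8.5.3.1 use similar wording.

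**The concern.** The analysis rule asks for a sample at a time when none is scheduled. A patient whose BCR-ABL1 meets the loss criterion at two, three or more successive 12-weekly visits has plainly lost MMR. If nobody redraws at 4 to 6 weeks, that patient still has no confirmed loss, stays in the risk set and is eventually censored as though still responding. No rule covers a repeat sample taken outside the window.

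Three secondary results depend on this: duration of MMR, duration of MR4 without loss of MMR (which SAP 2.6.2 analyses in the same way) and TTF. The possible error runs in one direction, towards longer durations. Whether a loss counts also depends on a site's redraw habits, which are unrelated to the drug.

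The dose-escalation wording makes the mismatch visible. Read on its own, it would let two 12-weekly PCRs establish confirmed loss for escalation while the same two results establish nothing for the analysis.

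**Working it through.** **The plan's own figure.** The documents give no calculation for loss of MMR. Their one design calculation reproduces: with N = 156, null 23%, alternative 33% and one-sided 0.025, the exact test rejects at 47 or more responders (30.1%), with exact alpha 0.0241 and power 0.801 against the stated 80%. Loss of MMR does not enter it.

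**Step 1: can two scheduled PCRs meet the window?**

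- Required gap: 4 to 6 weeks = 28 to 42 days. Reading the phrase as any time up to 6 weeks leaves the upper limit at 42.
- Nominal gap from Week 12: 12 × 7 = 84 days.
- Week 24 onwards: shortest 84 − 7 − 7 = 70 days; longest 84 + 7 + 7 = 98 days.
- Week 12 to Week 24: shortest 84 − 2 − 7 = 75 days; longest 84 + 2 + 7 = 93 days.
- Shortfall: 70 − 42 = 28 days, even for the closest permitted pair.

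No pair of consecutive on-schedule PCRs qualifies.

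**Step 2: what else can produce a loss event?**

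- An unscheduled draw in the window: permitted, not required.
- The exemptions. After baseline, marrow is scheduled only at Week 48 and at EOT for lack or loss of response (protocol 8.3.1.2). Loss of CHR must have led to discontinuation for lack of efficacy (SAP 5.4.3). A purely molecular relapse will often meet neither.
- An early-discontinuation EOT PCR that happens to fall 4 to 6 weeks after the first loss.
- A loss first seen at the EOT visit cannot be confirmed afterwards, because SAP 2.1.1 excludes post-EoT samples from these analyses.

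**Step 3: how large could the effect be?** Assumptions, none from the documents: true loss L by 96 weeks after first MMR, constant hazard, PCR every 12 weeks, losses persist, no other censoring, and a share q of losses redrawn in the window.

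*Scenario A*, one chance of a redraw, at first detection: reported proportion still in MMR = 1 − qL.

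*Scenario B*, a fresh chance q at each later visit still showing loss, event dated at the visit that is confirmed. With 8 visits in 96 weeks and r = (1 − L)^(1/8): reported proportion = (1 − L) + Σ (r^(j−1) − r^j)(1 − q)^(9−j), summed over j = 1 to 8.

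| L | True | q | A | B |
|---|---|---|---|---|
| 20% | 80% | 100% | 80% | 80% |
| 20% | 80% | 75% | 85% | 80.8% |
| 20% | 80% | 50% | 90% | 82.3% |
| 20% | 80% | 25% | 95% | 86.5% |
| 20% | 80% | 0% | 100% | 100% |
| 10% | 90% | 50% | 95% | 91.2% |
| 30% | 70% | 50% | 85% | 73.3% |

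A simulation of 40,000 responders gave 82.5% for Scenario B at L = 20%, q = 50%, which agrees with the formula within simulation error.

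**The case against.** The best defence is that the protocol foresees the redraw. Protocol 8.4.2 names confirmation of a loss of response as a purpose of unscheduled draws, protocol 8.3.1.1 tells sites about the 4 to 6 week repeat, and the SAP uses the results. The escalation wording can be read together with that rule. For a loss first seen at Week 108, escalation by Week 120 needs confirmation beforehand, which gives sites a practical reason to redraw. All this stands, and it rules out saying that duration *is* overstated: with every loss redrawn in time, there is no bias. It does not close the gap, because the draw is discretionary. Where protocol 8.3.1.1 wants a repeat for a missing or unanalysable PCR, it makes one mandatory within 4 weeks.

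Four stronger readings are tempting and are not supported:

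- *Every loss event needs a discretionary draw.* The exemptions and an early EOT PCR are other routes, and AP/BC and CML-related death end duration of MMR in their own right.
- *Half of the true events are missed.* That is one assumed value of q under Scenario A.
- *First losses never count.* Under the duration definition in SAP 5.4.1, which omits *confirmed*, they could. The under-count follows from 2.6.1.1 and 2.6.2, so the conflict is itself part of the problem.
- *The primary result is compromised.* Sample size and power do not use loss of MMR. The estimand does exclude patients who met treatment-failure criteria before Week 48, and SAP 5.4.4 lists confirmed loss among them. That matters only for someone who gains, loses and regains MMR by Week 48, and the documents give no frequency for this.

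It is also fair that these are untested secondary endpoints in a non-comparative trial, and that TTF has other event routes.

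**Conclusion.** The concern holds in limited form. It is certain from the schedule that consecutive scheduled PCRs cannot confirm a loss: the closest permitted pair misses the limit by 28 days. Under SAP 2.6.1.1 and 2.6.2, a persistent loss without a timely redraw, an exemption or a well-timed early EOT sample is not an event. Duration of MMR, duration of MR4 without loss of MMR and TTF may therefore be overstated, and never understated, by this rule.

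The size is unknown because q is unknown. At an assumed 20% true loss by 96 weeks, the overstatement runs from 0 to 20 percentage points, and from about 2 to 10 points if half of losses are redrawn. These figures illustrate the mechanism and do not forecast it. The change is worth making because the rule is stated, the remedy is cheap and the bias depends on site behaviour.

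**What to change.** 1. Use one event definition for duration of MMR throughout SAP Table 1-1, 2.6.1.1, 2.6.2 and 5.4.1, and apply it to duration of MR4 without loss of MMR and to the loss-of-MMR component of TTF.
2. Count a loss as confirmed when the next evaluable PCR, scheduled or unscheduled, at least 4 weeks later and with no 6-week upper limit, also meets the loss criterion. Keep the existing exemptions.
3. Date the event at the first of the two samples.
4. Add a sensitivity analysis counting unconfirmed losses as events, including those followed by discontinuation without a further PCR. This should not be the main analysis: a single unconfirmed rise before stopping for an adverse event would count as a loss, which biases the other way.
5. State whether the revised definition also applies to the treatment-failure list in SAP 5.4.4, since the primary estimand refers to those criteria.
6. The sponsor should reconcile the confirmation rule with the two-consecutive-tests wording in protocol 6.1, 6.6.2 and 8.5.3.1.

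**Cost.** SAP wording and one extra analysis, with no new visits or samples. Duration of MMR may look slightly less favourable. The definition departs from protocol 8.3.1.1, so it must be recorded in SAP Section 4, which at present lists no changes. Primary sample size and power stay as they are.

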5.4.2 Cytogenetic response

Cytogenetic response will be based on the percentage of Ph+ metaphases in the bone marrow. Cytogenetic evaluations will be considered for response assessment only if the number of metaphases examined is ≥ 20 in each bone marrow sample.

Cytogenetic response is categorized as follows (a review of a minimum of 20 metaphases is required):

- Complete response (CCyR): 0% Philadelphia chromosome positive (Ph+) metaphases
- Partial response (PCyR): >0 to 35% Ph+ metaphases
- Major response (MCyR = CCyR + PCyR): 0 to 35% Ph+ metaphases
- Minor response (mCyR): >35 to 65% Ph+ metaphases
- Minimal response: >65 to 95% Ph+ metaphases
- None: >95 to 100% Ph+ metaphases.

If bone marrow aspirate blast percentage is provided as ' $<X$ ' (i.e. below limit of detection), the numeric value is set to X for summary tables. In the listing ' $<X$ ' will be presented.

Complete cytogenetic response (CCyR)

CCyR is defined as a value of 0% Ph+ metaphases in bone marrow.

CCyR will be considered as a binary variable with subjects achieving CCyR grouped as 'responders' and subjects not achieving CCyR, subjects with missing cytogenetic evaluations grouped as 'non-responders'. In case no bone marrow aspirate was performed but the subject is in MMR at a specific time-point, the subject is considered to have achieved CCyR at that time-point. The date of CCyR is imputed by the date of MMR at the same scheduled time-point.

5.4.3 Hematologic response

Loss of CHR

Loss of CHR is defined by meeting any of the following:

- WBC count $> 20 \times 10^9/L$
- Platelet count $\geq 600 \times 10^9/L$
- Appearance of blasts or promyelocytes in peripheral blood
- Appearance of myelocytes + metamyelocytes $\geq 5\%$ in peripheral blood
- Progressive splenomegaly refractory to therapy (i.e. $\geq 5\text{cm}$ below left intercostal margin)

Loss of CHR must have led to treatment discontinuation because of lack of efficacy.

In addition, CML-related death or progression to AP or BC will be considered as loss of CHR in any case (if they occurred on treatment).

Complete hematologic response (CHR)

CHR is defined when all of the following criteria are present at any assessment which is confirmed by another assessment at least after 4 weeks:

- White blood cells (WBC) count $< 10 \times 10^9/L$
- Platelet count $< 450 \times 10^9/L$
- Basophils $< 5\%$
- No blasts and promyelocytes in peripheral blood
- Myelocytes + metamyelocytes $< 5\%$ in peripheral blood
- No evidence of extramedullary disease, including spleen and liver. As extramedullary disease is evaluated less frequently than hematology, the results of these evaluations are carried forward until the next assessment (unless extramedullary disease was not present at the current assessment but present at the next).

5.4.4 Treatment Failure

In the event of treatment failure the subject should be discontinued from the study treatment. The ELN criteria 2020 do not make provisions for treatment failure in 3rd line however they define that a level of BCR::ABL1 $> 1\%$ IS and failure to achieve CCyR is not sufficient for optimal survival. The following events will constitute ‘treatment failure’:

- BCR::ABL1 $> 1\%$ IS at 48 weeks after initiation of therapy or no complete cytogenetic response at 48 weeks.
- Subject demonstrates new T315I mutation.
- Subject shows lack or loss of response such as “Loss of CHR, CCyR or PCyR at any time after initiation of therapy OR confirmed loss of MMR”.
- Progression to AP/BC.
- Subjects fulfilling treatment failure criteria above but without alternative treatment options may however be continued on study drug if in the investigators opinion they are obtaining benefit from the drug. Subjects with BCR::ABL 1 greater than 10%

after 48 weeks of treatment or subjects with signs of progression to AP and BC must however be discontinued.

- Subjects with newly emerging T315I mutation and lack or loss of response. While asciminib has known activity against CML with additional T315I mutation, the recommended dose of 200 mg bid for the treatment of T315I is not in use in the study. In case a subject demonstrates a new T315I mutation on asciminib, subjects should not continue in the study.

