1. ***pre-treatment period:*** from day of subject’s informed consent to the day before first administration of study treatment
2. ***on-treatment period:*** from date of first administration of study treatment to 30 days after date of last administration of study treatment (including start and stop date).
3. ***post-treatment period:*** starting at day 31 after last administration of study treatment.

If dates are incomplete in a way that clear assignment to pre-, on-, post-treatment period cannot be made, then the respective data will be assigned to the on-treatment period.

Safety summaries (tables, figures) on the corresponding Safety set include only data from the on-treatment period with the exception of baseline data which will also be summarized where appropriate (e.g. change from baseline summaries). In particular, summary tables for adverse events (AEs) will summarize only on-treatment events, with a start date during the on-treatment period. In addition, a separate summary for death will be provided.

However, all safety data (including those from the pre-treatment and post-treatment) will be listed and flagged as appropriate.

Efficacy summaries on the FAS and FAS 2 (apart from OS and PFS) include data from baseline up to either the last assessment on or before the End of Treatment (EoT) visit or before or on treatment failure, whichever is the earliest.

The efficacy assessments collected post-treatment failure or post-EoT visit are not included in any efficacy analyses (except for OS and PFS analyses). However, they will be listed and flagged as appropriate.

Windows for multiple assessments

Data such as molecular response, cytogenetic response collected over time (including unscheduled visits) will be summarized by scheduled time point. As subjects do not always adhere to the visit schedule, visits will be remapped according to visit windows defined in Tables 2-1 to Table 2-3 of this document to enable by-visit analysis. Only those protocol-defined visits will have the visit window defined. Each assessment (including the end of treatment assessment), either scheduled or unscheduled, will have a mapped visit assigned, as long as study day is available, according to the defined visit window up to the date with data included.

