2.6.1.3 Other secondary efficacy endpoints

Time to treatment failure (TTF) is defined as the time from date of randomization to an event of treatment failure define as BCR::ABL1 > 1% IS. The following events will constitute ‘treatment failure’ for analysis purpose, and are based on the ELN criteria 2020 defining failure of a second line treatment adapted to include discontinuation of randomized treatment as an event:

- BCR::ABL1 >1% IS at 48 weeks after initiation of therapy or no complete cytogenetic response at 48 weeks.
- Subject demonstrates new T315I mutation
- Subject shows lack or loss of response such as “Loss of CHR, CCyR or PCyR at any time after initiation of therapy OR confirmed loss of MMR”
- Progression to AP/BC

For subjects who have not reached treatment failure, their TTFs will be censored at the time of last study assessment (PCR, cytogenetic, hematologic or extramedullary) before the cut-off date.

TTF (in months) is calculated as: (date of treatment failure or censoring date (see [Section 2.6.2](#)) - date of randomization + 1)/30.4375.

Progression-Free-Survival (PFS) is defined as the time from the date of randomization to the earliest occurrence of documented disease progression to AP/BC or the date of death from any cause before the cut-off date. The time will be censored at the date of last study assessment (PCR, cytogenetic, hematologic or extramedullary) or last post-treatment follow-up for subjects without event.

PFS (in months) is calculated as: (date of disease progression/death or censoring date (see [Section 2.6.2](#)) - date of randomization + 1)/30.4375.

Overall survival (OS) is defined as the time from the date of randomization to the date of death. Subjects who are alive at the time of the analysis data cutoff date will be censored at the date of last contact (see [Section 2.1.1](#)) before the cut-off date. OS (in months) is calculated as: (date of death or censoring date (see [Section 2.6.2](#)) - date of randomization + 1)/30.4375.

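### Read together, the SAP's rules turn a missing or inadequate Week-48 marrow into a treatment failure, adding an unsupported TTF event and discarding later PCR results from secondary efficacy analyses

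*SAP*

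**What the plan says.** Four rules in the SAP bear on the point.

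- **CCyR status.** SAP 5.4.2 admits a marrow on a minimum count: "Cytogenetic evaluations will be considered for response assessment only if the number of metaphases examined is" at least 20. CCyR is then binary, with "subjects with missing cytogenetic evaluations grouped as 'non-responders". One exception is given: "In case no bone marrow aspirate was performed but the subject is in MMR at a specific time-point", CCyR is taken as achieved.
- **Failure event.** SAP 5.4.4 lists "BCR::ABL1 $> 1\%$ IS at 48 weeks after initiation of therapy or no complete cytogenetic response at 48 weeks". SAP 2.6.1.3 repeats the item within the TTF definition, introduced by "The following events will constitute ‘treatment failure’ for analysis purpose". Neither section asks for an evaluable marrow.
- **Data cut.** SAP 2.1.1 states: "The efficacy assessments collected post-treatment failure or post-EoT visit are not included in any efficacy analyses", with OS and PFS excepted.
- **No assessment at a visit.** SAP 2.6.2 scores a subject with no available assessment at a time point as a non-responder at that time point.

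The protocol's own TTF event list (12.5.1) has no item for absence of CCyR. Protocol 9.1.1, on stopping study treatment, does have one. SAP section 4 reports no change to protocol-specified analyses.

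**The concern.** Counting missing data as non-response is conservative for a response rate. In the definition of a failure event the same convention creates an event from a sample that was never taken or could not be read.

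The subjects affected are those with BCR::ABL1 above 0.1% and up to 1% at Week 48. Above 1% they fail on PCR whatever the marrow shows. At or below 0.1% with no aspirate they are covered by the MMR exception. In between, the marrow decides.

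The consequence goes beyond TTF. These subjects are not in MMR at Week 48, so under protocol 6.6.2 they may be considered for escalation from Week 60. SAP 2.5.6 plans MMR rates at Weeks 96 and 144 in escalated subjects. The data cut removes the PCR results which that analysis needs.

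**Working it through.** **The plan's own figure.** Protocol 12.8.1 and SAP section 3 state 80% power for N = 156, null 0.23, alternative 0.33, one-sided 0.025. By the exact binomial, the smallest r with P(X ≥ r | 156, 0.23) ≤ 0.025 is 47, where the tail is 0.0241. P(X ≥ 47 | 156, 0.33) = 0.801, so the figure reproduces. It rests on Week-48 MMR, where a subject above 0.1% is already a non-responder, so nothing below changes it.

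**The rules applied at Week 48** (looking only at the PCR and CCyR item of the failure list):

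| BCR::ABL1 | Marrow | CCyR status | Failure? | Later PCR |
|---|---|---|---|---|
| >1% | any | – | yes, on PCR | excluded |
| >0.1% to 1% | ≥20 metaphases, 0% Ph+ | yes | no | used |
| >0.1% to 1% | ≥20 metaphases, >0% Ph+ | no | yes, on evidence | excluded |
| >0.1% to 1% | none, or <20 metaphases | no, by rule | yes, without evidence | excluded |
| ≤0.1% | not performed | yes, by MMR exception | no | used |
| ≤0.1% | performed, <20 metaphases | exception does not literally apply | yes, if read literally | excluded |

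The fourth row is the point. The last row is a side gap, because the exception is worded for an aspirate that was not performed.

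**Effect by endpoint for the fourth row**

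- TTF: one added event. No failure date is defined when there is no marrow. The Week-60 PCR (target Day 60 × 7 + 1 = 421) could be kept or lost depending on whether failure is dated at Day 337 or at the end of the window, Day 420.
- MMR, MR4 and MR4.5 at Weeks 72, 96 and 144: later results are unavailable, so non-response.
- Cumulative rates: a response first reached after failure is not counted.
- Time to MMR: a subject with no MMR before failure is censored at the last usable PCR, at or before Week 48.
- Duration of MMR: a subject whose first MMR comes after failure does not enter. One with MMR before Week 48 stays in.
- Escalated subjects at Weeks 96 and 144 (SAP 2.5.6): the data are excluded.

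**Size.** Let q be the share of the 156 at >0.1% to 1% at Week 48, m the share of those without a usable marrow, and r the share of those in MMR at a given later visit. The documents give none of the three. The ranges below are assumptions.

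- Subjects made failures = 156 × q × m
- Later MMRs lost = 156 × q × m × r
- Loss in the MMR rate = q × m × r

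| q | m | r | Failures | MMRs lost | Loss (points) |
|---|---|---|---|---|---|
| 0.20 | 0.05 | 0.20 | 1.6 | 0.3 | 0.2 |
| 0.30 | 0.10 | 0.20–0.40 | 4.7 | 0.9–1.9 | 0.6–1.2 |
| 0.40 | 0.40 | 0.40 | 25.0 | 10.0 | 6.4 |

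One lost MMR is 1/156 = 0.64 percentage points, whatever the assumptions.

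**The case against.** **The link is inferred.** SAP 5.4.2 defines a response variable, and SAP 5.4.4 and 2.6.1.3 neither refer to it nor mention missing marrows. SAP 5.5.1 keeps no response and missing as separate categories, and splits missing into ongoing subjects with and without treatment failure. A programmer could reasonably require an evaluable marrow. This stands in part: a reader might infer that the SAP states outright that a missing marrow is a failure, and it does not. But SAP 5.5.1 governs how responses are tabulated, and nothing exempts a missing marrow from the failure definition. SAP 5.4.2 is the only place that says who lacks CCyR.

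**It should be rare.** Protocol 8.1 makes the Week-48 aspirate mandatory even when no baseline sample exists, and SAP Table 2-2 accepts one from Day 253 to Day 420, about 12 weeks either side of Day 337. One remote visit at Week 48 does not make the marrow missing. This stands and tells against the upper end of the assumed ranges. It limits how often the rule bites without removing it. The off-site procedures in protocol 8.4 do not include marrow, and inadequate samples can still occur.

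**Little depends on it.** The affected endpoints are secondary and untested, and the error runs against the drug. This also stands. A reader might infer that the primary result is biased or efficacy inflated. For these subjects neither follows: they are already Week-48 non-responders, and the effect is more TTF events and fewer late responses. One narrow route to the primary endpoint exists in other subjects. If both the Week-48 PCR and the marrow are missing, a failure dated at Week 48 would remove the Week-60 PCR that the imputation in SAP 2.5.4 needs.

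**The data cut is the deeper cause.** SAP 2.1.1 also removes later PCR results from genuine failures who stay on treatment. That is true and is a wider question. It does not justify creating failures from absent samples.

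**Conclusion.** The concern holds as a consequence of reading SAP 5.4.2 with 2.6.1.3, 5.4.4 and 2.1.1. Followed literally, these sections create TTF events without cytogenetic evidence and understate late molecular response, including in the escalation analysis. Because two readings are open and give different results, the derivation should be settled in the SAP.

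The frequency is unknown. The span of about 2 to 25 subjects rests wholly on assumed shares and should not be read as an estimate. Given the mandatory marrow and wide window, the true number may be near or below the low end.

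It would be too strong to say that affected subjects drop out of time to MMR. They remain in the FAS and are censored. Nor do the documents show that subjects in this band are those most likely to reach MMR late.

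**What to change.** Change the analysis derivation only, that is, SAP 2.6.1.3 and the failure flag used in SAP 2.1.1:

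1. Count the cytogenetic component as an event only when an evaluable Week-48 marrow (at least 20 metaphases) shows more than 0% Ph+ metaphases. Every such event then has a sample date.
2. Judge subjects with a missing or non-evaluable marrow on BCR::ABL1 and the other listed failure events.
3. Keep missing as non-response for the CCyR rate only.
4. List the subjects with missing or non-evaluable Week-48 marrows.
5. Reconcile the TTF event lists in protocol 12.5.1 and SAP 2.6.1.3, and record the difference in SAP section 4.

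Leave the discontinuation text in protocol 9.1.1 as it is. SAP 5.4.4 repeats that text, so a cross-reference there should say that the analysis flag follows SAP 2.6.1.3.

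The cost is a few sentences, one derivation change and one listing, with no new data. The downside is that a true cytogenetic failure with no marrow and BCR::ABL1 at or below 1% would not be counted. The listing in step 4 shows how many subjects that could concern.
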